#### **Secondary outcomes**

Secondary measures are meant to capture effects on dimensions that relate to reductions in violent behaviour, either because they are simultaneously affected by the intervention and support/reinforce effects on violent behaviour, or because they may reveal some of the

mechanisms through which violent behaviour is affected in the short and longer terms. We add a measure of offending behaviour to the list of secondary outcomes, which directly informs on the main goal of the intervention of reducing violence.

Criminal activity: measured by an indicator for a recorded arrest during the period of 16 months following recruitment. This time lag provides some scope for criminal activity to happen and be registered in policy records, which explains why this one outcome is measure later than all others. The PNC measure of criminal activity is an objective measure of offence activity and provides direct evidence on the key goal of the programme of reducing violence among young people most at risk of violent behaviour. Two features of these data explain that it is considered as a secondary outcome. First, the necessary delays in obtaining data on criminal activity, which at the earliest will be available in full only 2 years after the end of the trial, significantly extending the time required to produce key findings and learnings. And second, the low frequency of detectable criminal activity significantly increases the risk that the study would be under-powered to identify any effects given current projections of the size of the trial.

Data on recorded offences will be obtained from the Policy National Computer database, and linked to experimental data through the use of participant's name, LA and date of birth.

Self-reported and practitioner-reported perceptions of young person's safety: measures taken from the young person and practitioner versions of "Checkpoint: A safety scale for young people", which is part of the endline young person's survey taken in week 20 after recruitment and which was co-developed by the project and evaluation teams during the pilot phase of this project. Subjective measures of propensity to commit violent acts or of being vulnerable to being a victim of violence, provides an alternative view on the impact of the intervention on violent behaviour. Since it can signal changes in attitudes towards violent behaviour, these measures may also be especially informative about long-lasting effects of the intervention.

Wellbeing: measured by the Short Warwick–Edinburgh Mental Well-being Scale (SWEMWBS), which is part of the endline young person's survey taken in week 20 after recruitment (Ng Fat et al. 2017). Feeds directly into the logic model as one of the expected outcomes from the intervention.

Emotional self-regulation: measured by the Self-regulation subscale from the Trait Emotional Intelligence Questionnaire – Adolescent Short Form (TEIQUE-ASF), which is part of the endline young person's survey taken in week 20 after recruitment. Captures aspects of emotional difficulties that the logic model predicts will be affected by the intervention.

Social connectedness: measured by the Social Connectedness Scale – Revised (SCS-R), which is part of the endline young person's survey taken in week 20 after recruitment. This scale will

help measure whether the intervention increases the young person's resilience through strengthened sources of social support (at home, at school if relevant, and elsewhere).

Internalising behaviours: emotional difficulties and peer difficulties subscales of the SDQ measured at baseline and endline as part of the participant's surveys administered following recruitment and at week 20 after recruitment respectively.

Hyperactivity: hyperactivity subscale of the SDQ measured at baseline and endline as part of the participant's surveys administered following recruitment and at week 20 after recruitment respectively.

Prosocial behaviour: measured by the prosocial scale of the Strengths and Difficulties Questionnaire, which is part of the endline young person's survey taken in week 20 after recruitment. This measure will provide insight into whether the impact of the intervention may be partly driven by changes in prosocial behaviour, as hypothesized in the logic model.

Prosocial identity: measured by the Pro-social Identity Scale (PIDS), which is part of the endline young person's survey taken in week 20 after recruitment. This measure will provide insight into whether the impact of the intervention may be partly driven by changes in prosocial identity, as hypothesized in the logic model.

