However, qualitative data also revealed that some allocators considered potential benefits and perceived level of risk in deciding how to allocate young people to teams, a practice that violates the principles of the evaluation design (which is based on the assumption that assignment to teams is based on team capacity at the time the young person is referred to the services, with one exception for young people who are returning to LA services after a brief interruption, and who are assigned to the same team they were previously). The consequences of considering potential benefits from Your Choice in determining assignment are not evident from observed pilot data on baseline characteristics (as far as we can say, observed characteristics are well balanced across treatment arms), but the suggestive evidence of its (however sparse) use prompted us to reinforce the training of Local Authorities staff ahead of efficacy around the efficacy trial and especially the importance of rigorously following the RCT design at all stages of delivering Your Choice for the purpose of the evaluation.

- Session forms and qualitative data reveal that the intervention was implemented with fidelity, with those assigned to teams delivering Your Choice receiving a more intense schedule of meetings that were more geared towards CBT methods and contained different content as compared to BAU.
- The recruitment of young people into the pilot study was lower than anticipated. This affects our expectations about the size of the experimental group during the efficacy trial, and is reflected in the power calculations detailed later in this report.
- The sharing of data between councils and evaluators was carried out at irregular time intervals and sometimes with severe delays; this was particularly the case with process data collected through session forms (required for the implementation and process evaluation). The collection of endline survey information, both from young people and practitioners, was also patchy and often delayed. These concerns about the data prompted us to develop a new online mobile-optimised interface for practitioners to use to fill out forms in a much easier and faster way than during the pilot and for SPOCs to supervise data collection in real-time. Moreover, to improve the timely collection of

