Baseline for secondary	variable	Social connectedness score, internalising behaviour, hyperactivity, prosocial behaviour and prosocial identity, self-reported and practitioner-reported perceptions of young person's safety,
outcomes	measure (instrument, scale, source)	Social connectedness: The Social Connectedness Scale – Revised (SCS-R), survey of young person following consent before Your Choice starts (in some cases, some form of BAU work/support will have

already been taking place). Measured as part of the baseline participant's survey, administered in week 1 after recruitment, before the start of Your Choice.

Internalising behaviours: emotional difficulties and peer difficulties subscales of the SDQ measured at baseline and endline as part of the participant's surveys administered following recruitment and at week 20 after recruitment respectively.

Hyperactivity: hyperactivity subscale of the SDQ measured at baseline and endline as part of the participant's surveys administered following recruitment and at week 20 after recruitment respectively.

*Prosocial behaviours*: Strength and Difficulties prosocial behaviour subscale measured at baseline and endline as part of the participant's surveys administered following recruitment and at week 20 after recruitment respectively.

Prosocial identity: Pro-social Identity Scale (PIDS) measured at baseline and endline as part of the participant's surveys administered following recruitment and at week 20 after recruitment respectively.

Self-reported and practitioner-reported perceptions of young person's safety: Young person and practitioner versions of "Checkpoint. A safety scale for young people", which is an instrument to measure young people's perceptions of safety developed by the research team. Measured as part of the baseline young person and practitioner surveys, administered at week 1 after recruitment.

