Step 3. Main analysis, which will be a linear probability model to measure the impact of Your Choice on an indicator for high to very high conduct problems (primary outcome). The regression will also control for the baseline outcome and any controls for which we find statistically significance imbalances in step 1, as well as Local Authority fixed effects. Standard errors will be clustered at the Local Authority level, following Chaisemartin and Ramirez-Cuellar (2022). Effects will be shown in percentage points and as a percent change relative to the baseline average frequency of young people in the high to very high range for this population. We will show the 95% confidence interval for the estimated effect. This analysis will directly address research question 1.

Step 4. Robustness analysis of estimated effects on primary outcome. This will involve estimating alternative versions of the primary regression model using a post-double selection

LASSO to identify variables that are related with both the treatment status and the primary outcome. We will consider relevant contextual, demographic, personal and environmental information as described in step 1. This analysis will provide further support for the findings in the main analysis (step 3).

Step 5. Steps 3 and 4 will be repeated for the secondary outcomes measuring whether the young person got arrested at any point during the 16 months following recruitment into Your Choice (PNC data), and risk assessments by the young person and practitioner at endline (survey completed at week 20 after recruitment). Effects on arrest probabilities will be shown in percentage points and as a percent change relative to frequency of arrests among the control group over the same period. Effects on risk levels will be shown in standard deviation units. Standard errors will be clustered at the local authority level and we will show the 95% confidence interval for the estimated effect. This analysis will address research question 2.

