*Wellbeing*: The Short Warwick–Edinburgh Mental Well-being Scale (SWEMWBS). Part of the endline young person questionnaire, which is administered at some point between weeks 14 and 20 after recruitment.

*Emotional self-regulation*: Trait Emotional Intelligence Questionnaire – Adolescent Short Form (TEIQUE-ASF) – Self regulation subscale. Part of the endline young person questionnaire, administered at week 20 after recruitment.

Social connectedness: Social Connectedness Scale – Revised (SCS-R). Part of the endline young person questionnaire, administered at week 20 after recruitment.

Internalising behaviours: emotional difficulties and peer difficulties subscales of the SDQ measured at baseline and endline as part of the participant's surveys administered following recruitment and at week 20 after recruitment respectively.

*Hyperactivity*: hyperactivity subscale of the SDQ measured at baseline and endline as part of the participant's surveys administered following recruitment and at week 20 after recruitment respectively.

*Prosocial behaviours*: Strength and Difficulties prosocial behaviour subscale measured at baseline and endline as part of the participant's surveys administered following recruitment and at week 20 after recruitment respectively.

*Prosocial identity*: Pro-social Identity Scale (PIDS) measured at baseline and endline as part of the participant's surveys administered following

		recruitment and at week 20 after recruitment respectively.	
	variable	Conduct problems	
Baseline for primary outcome	measure (instrument, scale, source)	Indicator for scoring in the high or very high range of conduct problems scale from the Strengths and Difficulties Questionnaires.	
		Measured as part of the baseline participant's survey, administered in week 1 after recruitment, before the start of Your Choice.	
	variable	Social connectedness score, internalising behaviour, hyperactivity, prosocial behaviour and prosocial identity, self-reported and practitioner-reported perceptions of young person's safety.	
	measure (instrument, scale, source)	All measured as part of the baseline participant's survey, administered in week 1 after recruitment, before the start of Your Choice.	
Baseline for secondary		Social connectedness: The Social Connectedness Scale – Revised (SCS-R), survey of young person following consent before Your Choice starts (in some cases, some form of BAU work/support will have already been taking place).	

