#### Secondary outcome analysis

Analysis of secondary outcomes will follow the same approach as for primary outcomes described above. To account for multiple hypothesis testing given the large number of secondary outcomes, we will calculate p-values using the step-down procedure of Romano and Wolf [2016]. The Romano-Wolf correction (asymptotically) controls the familywise error rate (FWER), that is, the probability of rejecting at least one true null hypothesis in a family of hypotheses under test. This correction is considerably more powerful than earlier multiple testing procedures such as the Bonferroni and Holm corrections, given that it takes into account the dependence structure of the test statistics by resampling from the original data. To implement it, we will use Stata's rwolf2 command, report unadjusted and adjusted *p*-values, and determine statistical significance of the results based on adjusted *p*-values below 0.05.

The estimating equation for ITT impacts for young period i will be of the form:

$$Y_{i1} = \beta_0 + \beta_1 D_i + \beta_2 X_i + \beta_3 Y_{i0} + strata \ fixed \ effects + u_i$$

where, as before,  $Y_{i1}$  is the secondary outcome of interest, and  $Y_{i0}$  is the baseline value for that same outcome (if any),  $D_i$  is an indicator for treatment assignment,  $X_i$  are any baseline characteristics of the young person for which we find statistically significant imbalances between treated and control groups, and  $u_i$  is an error term.

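### The arrest model calls for a baseline control, but neither document defines a pre-recruitment arrest variable for adjustment or balance checking

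*Protocol*

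**What the plan says.** **Outcome.** Protocol, Secondary outcomes: criminal activity is "measured by an indicator for a recorded arrest during the period of 16 months following recruitment". The records come from the PNC and are "linked to experimental data through the use of participant's name, LA and date of birth". No date range is given for the extract.

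**Baselines.** Protocol Table 1 (Design) gives the baseline variables for secondary outcomes as "Social connectedness score, internalising behaviour, hyperactivity, prosocial behaviour and prosocial identity, self-reported and practitioner-reported perceptions of young person's safety". The SAP's Design overview repeats the list, starting "Social connectedness score, internalising behaviour, hyperactivity, prosocial behaviour and prosocial identity", and describes the measures as "All measured as part of the baseline participant's survey, administered in week 1 after recruitment, before the start of Your Choice". Offending is in neither list.

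**Model.** Protocol, Analysis, Step 5: "Steps 3 and 4 will be repeated for the secondary outcomes measuring whether the young person got arrested". Step 3 controls for the baseline outcome, for covariates found imbalanced in Step 1, and for Local Authority (LA) fixed effects. In the SAP's Secondary outcome analysis, the baseline term "is the baseline value for that same outcome (if any").

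**Balance and robustness.** Protocol Step 1 lists demographics, main activity, looked-after status, special educational needs, primary needs, SDQ and other survey measures, self-reported and practitioner risk assessments, and services. The SAP's Imbalance at baseline section is similar. Neither lists earlier arrests. The LASSO in Protocol Step 4 draws on the Step 1 information.

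**The concern.** Step 5 inherits a control for the baseline outcome, but for arrest there is nothing defined to put in that place. The SAP's conditional wording then lets the term drop without anyone deciding that it should.

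Two features of this trial give the gap some weight. First, teams are randomised but young people are not, and the pilot found that "some allocators considered potential benefits and perceived level of risk in deciding how to allocate young people to teams". The protocol's Compliance section accepts that selective assignment cannot be fully excluded. An arrest record from before recruitment is a direct and objective marker of prior risk. It does not depend on a rating by a practitioner who knows the arm, or on a questionnaire completed in that practitioner's session.

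Second, the protocol calls arrest a key secondary outcome, closely tied to the aim of reducing violence, and expects low frequency to limit power. A baseline that predicts later arrest would recover a little precision at no recruitment cost.

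**Working it through.** The documents give no arrest rate, minimum detectable effect (MDE) or power for arrest, so there is no figure of the plan's to reproduce. The check has two parts.

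**1. Is a baseline arrest variable defined anywhere?**

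| Place | Content for arrest |
|---|---|
| Protocol, Secondary outcomes | Window after recruitment only |
| Protocol Table 1 and SAP Design overview, baseline rows | Offending absent |
| Protocol Steps 3 and 5 | Baseline outcome to be controlled; not defined for arrest |
| SAP, Secondary outcome analysis | Baseline term only where one exists |
| Protocol Step 1 and SAP, Imbalance at baseline | No prior arrests |
| Protocol Step 4 (LASSO) | Candidates come from Step 1, so no prior arrests |
| SAP, Longitudinal follow-up analyses | Conditional linked extract for long-term follow-up, again after recruitment |

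No place defines or requests arrests before recruitment. No place rules them out either.

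**2. What could it be worth? (illustration)**

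Inputs from the SAP: Sample B in Table 5, 937 intervention and 626 control (total 1,563); power 0.80; two-sided alpha 0.05, used here without the Romano-Wolf correction. Assumptions: arrest rate p of 10% to 30%, correlation r between prior and later arrest of 0.2 to 0.5, design effect DE = 1.5, everyone linked.

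*Precision.* Adjustment multiplies residual variance by 1 − r², and hence the MDE by √(1 − r²):

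| r | 1 − r² | √(1 − r²) | Fall in MDE | Equivalent sample, 1/(1 − r²) |
|---|---|---|---|---|
| 0.2 | 0.96 | 0.980 | about 2% | 1.04 |
| 0.3 | 0.91 | 0.954 | about 5% | 1.10 |
| 0.4 | 0.84 | 0.917 | about 8% | 1.19 |
| 0.5 | 0.75 | 0.866 | about 13% | 1.33 |

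MDE = (1.96 + 0.84) × √[p(1 − p)(1 − r²) × DE × (1/937 + 1/626)]. With p = 10% and r = 0, this is 2.80 × √(0.09 × 1.5 × 0.002665) = 5.3 points.

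| p | MDE, r = 0 | MDE, r = 0.5 |
|---|---|---|
| 10% | 5.3 points | 4.6 points |
| 20% | 7.1 points | 6.1 points |
| 30% | 8.1 points | 7.0 points |

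These falls are upper limits: they ignore whatever LA fixed effects and other included covariates already explain.

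*Bias.* Shift = (difference between arms in prior-arrest prevalence) × (difference in later arrest risk by prior arrest).

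- 5 points × 0.20 to 0.40 = 1.0 to 2.0 points
- 10 points × 0.20 to 0.40 = 2.0 to 4.0 points

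With LA fixed effects, the imbalance that counts is the one within LAs. Any adjusted proxy for prior arrest would reduce the shift.

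**The case against.** A reader might infer that the arrest analysis cannot adjust for earlier arrests. The documents do not support that: the extract has no stated date limits, so a look-back can still be requested. Conversely, that the same linkage would return earlier arrests is a reasonable inference, not something either document says.

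A reader might also infer that selective allocation by risk is left unaddressed. That too goes further than the text. Practitioner risk rating, self-reported risk, SDQ scores, needs and services are balance-checked, controlled if imbalanced, and available to the LASSO. The LA workbook, completed by the LA's own data contact, adds referral reason and other services. The risk register plans a check on historical allocation data, and the Timeline schedules agreements for it with 3 to 4 LAs. The protocol also reports that observed characteristics were balanced in the pilot.

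The SAP's conditional baseline wording is not a slip in itself. Wellbeing and self-regulation are measured only at endline and need it. Finally, the protocol calls the crime analysis exploratory and expects full crime data no earlier than two years after the trial ends, well past the August 2025 report.

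All of this stands and limits the weight of the point. It does not close the gap: the proxies are not arrest records, their adjustment is conditional, the historical check covers a few LAs, and the baseline term in Step 5 remains undefined for arrest.

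**Conclusion.** The point holds as a gap in specification that is cheap to close. The protocol calls for a baseline control in the arrest model, neither document defines one, and the SAP wording lets it lapse. A prior-arrest measure would give an exploratory but key secondary outcome an objective pre-recruitment covariate and an added check on comparability.

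The possible bias is the stronger argument: 1 to 4 points under the assumed imbalances, against an illustrative unadjusted MDE of about 5 to 8 points. The precision gain is modest, an MDE lower by at most about 2% to 13%. Both ranges rest wholly on assumed correlations, imbalances and risk gaps. They do not show that the arrest estimate will be biased, and nothing in the documents shows that prior arrests differ between arms. The primary outcome has its own baseline control and is not affected.

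**What to change.** 1. In Protocol Table 1 and the SAP's Design overview, add a baseline for criminal activity: any recorded PNC arrest in the 16 months before recruitment.
2. Request that window in the PNC application already planned in the protocol's risk register, after checking that the privacy notice covers records from before recruitment.
3. In the SAP, name this variable as the baseline term Y_i0 in the arrest model, and offer it to the LASSO for the arrest outcome.
4. Report it by arm in a balance table when the PNC data arrive. Leave the week-20 analyses and their timetable unchanged.
5. If the look-back cannot be obtained, state that arrest has no baseline and that Step 5 omits the term.

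Cost: a wider date range in one data request, the privacy-notice check, and a few lines in each document. The youngest participants will probably have few earlier arrests, so the variable will say less about them.

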#### **Data**

For completeness and clarity it is worth briefly overviewing the data that will be available and the timing of data collection. More details can be found in the pilot report, with a copy of all questionnaires and of the session form available in Annex E of that report.

LA Workbook: Spreadsheet to be filled out by the SPOC/Data Lead of the Local Authority to provide background information about the young person, as well as a log of training dates for practitioners involved in the study and a log of clinical supervision sessions. The background information about the young person includes: date of birth, gender, ethnicity, SEN status, reason for referral into the service and any other services the young person is involved with. The workbook also includes a tab to list some basic demographic information (ethnicity, gender, age) about the young people who were approached to enter the study but who did not consent to and provides an option to explain the reason (if known) for non-consent.

Baseline young person questionnaire: The baseline young people survey is administered shortly after recruitment, in week 1, during a session with the assigned practitioner. It includes the Strengths and Difficulties Questionnaire (SDQ), a scale developed by the evaluation and project team about the young person's safety (young person Checkpoint), the Social Connectedness Scale — Revised (SCS-R), the Pro-Social IDentity Scale (PIDS) and a question about the young person's main activity at the time of the survey.

Baseline practitioner questionnaire: The baseline practitioner survey is completed shortly after recruitment, in week 1. It asks the young person's practitioner to report their risk rating of the young person, as well as their perception of the young person's safety using the practitioner version of Checkpoint.

Endline young person questionnaire: The endline young people survey is administered at the end of Your Choice period, in week 20 after recruitment, during a session with the assigned practitioner. It includes the same content as the baseline young person questionnaire, plus the following scales: The Short Warwick–Edinburgh Mental Well-being Scale (SWEMWBS), the Trait Emotional Intelligence Questionnaire – Adolescent Short Form (TEIQUE-ASF) – Self regulation subscale, and the Pro-Social IDentity Scale (PIDS). The latter were excluded from the baseline survey to keep it as short as possible while focusing on the most relevant measures, and also because these scales are most interesting as outcomes rather than as conditioning variables given the rich data we already collect at baseline. The endline questionnaire also asks the young person some questions about their experience working with their practitioner: it asks whether they would recommend it to someone else, it provides a free text box for any additional comments, and it asks a series of 7 questions about the practitioners' approach and practices to working with the young person. These approaches/practices were selected to be those most characteristic of the practices embedded in the Your Choice training.

Endline practitioner questionnaire: The endline practitioner survey is completed at the end of Your Choice period, in week 20 after recruitment. It includes the practitioner version of Checkpoint, as well as a series of 7 questions about the practitioners' approach and practices to working with the young person. These approaches/practices are the same as the ones asked to the young person in the endline questionnaire and were selected to be those most characteristic of the practices embedded in the Your Choice training.

Session forms: Practitioners are requested to fill out a session form every time they conduct a session with the young person or every time a session is cancelled. The session form asks a few details about the location of the session, the young person's level of engagement, whether the session was related to the Your Choice programme, and depending on the latter offers one or two dropdown menus to describe the content of the session. The practitioner is then offered a free text box to include any further comments on the session. If the session did not take place, the session form asks whether the reason for cancellation is known and offers a free text box to include any other details about the session that did not take place.

